Appendix G. CTCAE Grades

Test	Grade 1	Grade 2	Grade 3	Grade 4
SGPT/ALT increased	> ULN – 3.0 × ULN	> 3.0 – 5.0 × ULN	> 5.0 – 20.0 × ULN	> 20.0 × ULN
SGOT/AST increased	> ULN – 3.0 × ULN	> 3.0 – 5.0 × ULN	> 5.0 – 20.0 × ULN	> 20.0 × ULN
GGT increased	> ULN – 2.0 × ULN	> 2.5 – 5.0 × ULN	> 5.0 – 20.0 × ULN	> 20.0 × ULN
ALP increased	> ULN – 2.5 × ULN	> 2.5 – 5.0 × ULN	> 5.0 – 20.0 × ULN	> 20.0 × ULN
TBL increased	> ULN – 1.5 × ULN	> 1.5 – 3.0 × ULN	> 3.0 – 10.0 × ULN	> 10.0 × ULN
Creatinine [†] increased	> 1 - 1.5 x baseline (BL); > ULN – 1.5 × ULN	> 1.5 - 3.0 x BL; > 1.5 – 3.0 × ULN	> 3.0 x BL; > 3.0 – 6.0 × ULN	> 6.0 × ULN
Hemoglobin decreased	< LLN – 100.0 g/L	< 100.0 – 80.0 g/L	< 80.0 – 65.0 g/L	< 65.0 g/L
Neutrophil count decreased	< LLN – 1.5 × 10 ⁹ /L	< 1.5 – 1.0 × 10 ⁹ /L	< 1.0 – 0.5 × 10 ⁹ /L	< 0.5 × 10 ⁹ /L
WBC decreased	< LLN – 3.0 × 10 ⁹ /L	< 3.0 – 2.0 × 10 ⁹ /L	< 2.0 – 1.0 × 10 ⁹ /L	< 1.0 × 10 ⁹ /L
Lymphocyte count decreased	< LLN – 0.8 × 10 ⁹ /L	< 0.8 – 0.5 × 10 ⁹ /L	< 0.5 – 0.2 × 10 ⁹ /L	< 0.2 × 10 ⁹ /L

† If the calculation based on BL results in a different grade than the calculation based on ULN, use the higher grade.

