9.3.2.2 Assessment of Shift from Baseline in Clinical Laboratory Variables

The baseline and post-baseline laboratory observations will be categorized as Grade 0, Grade 1, Grade 2, Grade 3, and Grade 4 and shifts from baseline grade to worst on-therapy grade will be summarized. A similar shift table will be provided to summarize shifts from baseline to the final post-baseline value. Toxicity grading scale is based on CTCAE version 4.03. Shift tables from baseline according to the grades will be provided for laboratory variables including SGPT/ALT, SGOT/AST, GGT, ALP, total bilirubin, creatinine, hemoglobin, neutrophils count, WBC, and lymphocyte count.

Note that the minimum/maximum category is used, rather than the category of the minimum/maximum value. The two may be different due to variation in the reference range.

No statistical tests will be performed for this analysis.

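### SAP Appendix G leaves GGT values above 2.0 and up to 2.5 × ULN without a grade, so the planned GGT shift tables cannot classify them

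*SAP*

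**What the plan says.** SAP 9.3.2.2 sorts baseline and post-baseline laboratory values into Grades 0 to 4. It states that "shifts from baseline grade to worst on-therapy grade will be summarized" and adds a second table: "A similar shift table will be provided to summarize shifts from baseline to the final post-baseline value". The parameters are "laboratory variables including SGPT/ALT, SGOT/AST, GGT, ALP, total bilirubin, creatinine" and several haematology counts. The source is named: "Toxicity grading scale is based on CTCAE version 4.03". The section also states: "No statistical tests will be performed for this analysis".

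Appendix G gives the cut-offs. For GGT, Grade 1 runs from above ULN to 2.0 × ULN, Grade 2 from above 2.5 to 5.0, Grade 3 from above 5.0 to 20.0, and Grade 4 lies above 20.0. The ALP row has the same Grade 2, 3 and 4 bands, but its Grade 1 ends at 2.5 × ULN.

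For creatinine, Grade 1 is "> 1 - 1.5 x baseline (BL); > ULN – 1.5 × ULN" and Grade 2 is "> 1.5 - 3.0 x BL; > 1.5 – 3.0 × ULN". The footnote to that row resolves disagreement between the two criteria: "If the calculation based on BL results in a different grade than the calculation based on ULN, use the higher grade".

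**The concern.** A grading scale used for a shift table has to give every value a grade. The GGT row does not, and neither Appendix G nor 9.3.2.2 says what to do with a value between the two cut-offs. The programmer must choose Grade 0, 1, 2 or missing, and the choice changes the direction in which some subjects appear to move.

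Other outputs do not fill this gap for GGT. The liver-elevation thresholds in SAP 9.3.2.4 cover ALT, AST, bilirubin and ALP, not GGT. The GGT criterion in Table C-2 starts above 5.0 × ULN. The ANOVA in 9.3.2.1 compares means, not numbers of subjects. The shift tables are therefore the planned categorical display of mild to moderate GGT rises, in a trial whose Protocol Section 2.2 asks for follow-up of selected liver laboratory parameters.

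The creatinine row raises a separate and lesser point. Baseline compared with itself has ratio 1, so the baseline criterion alone can only move a subject upward, and any later value above baseline counts.

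**Working it through.** **1. Do the bands meet?** Input: the cut-offs in SAP Appendix G. Test: the bound that closes one grade must equal the bound that opens the next.

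| Row | Grade 1 to 2 | Grade 2 to 3 | Grade 3 to 4 |
|---|---|---|---|
| ALT, AST (× ULN) | 3.0 / 3.0 | 5.0 / 5.0 | 20.0 / 20.0 |
| **GGT (× ULN)** | **2.0 / 2.5** | 5.0 / 5.0 | 20.0 / 20.0 |
| ALP (× ULN) | 2.5 / 2.5 | 5.0 / 5.0 | 20.0 / 20.0 |
| Bilirubin (× ULN) | 1.5 / 1.5 | 3.0 / 3.0 | 10.0 / 10.0 |
| Creatinine (× ULN) | 1.5 / 1.5 | 3.0 / 3.0 | 6.0 / 6.0 |
| Creatinine (× baseline) | 1.5 / 1.5 | 3.0 / 3.0 | none |
| Haemoglobin (g/L) | 100 / 100 | 80 / 80 | 65 / 65 |
| Neutrophils (10⁹/L) | 1.5 / 1.5 | 1.0 / 1.0 | 0.5 / 0.5 |
| WBC (10⁹/L) | 3.0 / 3.0 | 2.0 / 2.0 | 1.0 / 1.0 |
| Lymphocytes (10⁹/L) | 0.8 / 0.8 | 0.5 / 0.5 | 0.2 / 0.2 |

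GGT is the only row with a gap.

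**2. What happens to a subject in the gap?** Take baseline 1.8 × ULN (Grade 1) and final value 2.3 × ULN.

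| Treatment of the ungraded value | Final-value table shows |
|---|---|
| Grade 0 | Grade 1 to 0, an apparent improvement |
| Missing | Subject has no final grade |
| Grade 1 (boundary at 2.5) | No shift |
| Grade 2 (boundary at 2.0) | Grade 1 to 2 |

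Either contiguous boundary removes the false improvement. The reverse also occurs: with ungraded values set to Grade 0, a fall from 2.3 to 1.8 × ULN reads as Grade 0 to 1. Baseline values in the gap are possible, because Protocol Section 5.1 limits AST, ALT and bilirubin but not GGT.

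The worst-value table is less exposed. SAP 9.3.2.2 takes the extreme category and not the category of the extreme value, so another on-therapy value above ULN and up to 2.0 × ULN would still give Grade 1. The same subject looks improved there only if no other on-therapy value earns a grade above 0.

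**3. How many subjects?** The documents give no GGT distribution, so no count can be computed.

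**4. Creatinine (secondary).** Grade = the higher of the baseline-based and ULN-based grades. With an assumed ULN of 110 µmol/L and baseline 60, a value of 61 is Grade 1, 90 is Grade 1 (90/60 = 1.5) and 91 is Grade 2.

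Protocol Appendix D schedules five post-baseline chemistry draws to Week 24 (Weeks 4, 8, 12, 16, 24). With no drug effect and exchangeable continuous values:

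- P(worst value above baseline) = 1 − 1/6 = 5/6 = 83%, or 175 of 210 per arm.
- P(final value above baseline) = 1/2, or 105 of 210.

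Reporting precision lowers these figures. The simulation below uses assumptions not found in the documents: median 72 and ULN 110 µmol/L, within-subject CV 3% to 8%, normal baseline, all five draws taken.

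| Rule and reporting step | Worst value, Grade ≥ 1 | Final value, Grade ≥ 1 |
|---|---|---|
| SAP rule, 1 µmol/L | 78% to 82% | 43% to 48% |
| SAP rule, 8.84 µmol/L | 32% to 63% | 14% to 31% |
| ULN only, all steps examined | about 1% to 4% | 0.3% to 1.2% |

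Grade 2 or higher from noise alone is about 0.1% or less. With CV 5% and 1 µmol/L steps, true rises of 0, 2, 5 and 10% give 46, 58, 73 and 90% at Grade ≥ 1 on the final-value table, and 80, 88, 96 and 99% on the worst-value table.

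**The case against.** The best defence is that little depends on these cells. The shift tables are descriptive, untested and read against concurrent placebo. GGT and creatinine are also compared by mean change with 95% confidence intervals (SAP 9.3.2.1) and by Grade 3+ and PCS criteria (SAP 9.3, 9.3.2.3, Appendix C), none of which use the boundaries in question. Liver safety rests mainly on ALT, AST, bilirubin and ALP, with a Hy's Law listing and an eDISH plot. The GGT gap looks like a slip of one number, and a programmer could settle it from the cited scale. All of this bears on size and stands. It does not give the undefined values a grade, and resolving a cut-off at programming is weaker than correcting it in the SAP.

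On creatinine the defence is stronger. The SAP adopts a named scale. Whether the row reproduces that scale cannot be checked from the documents; if it does, the rule belongs to the scale and is not an SAP error. Grading Grade 1 on ULN alone would also create an oddity: with baseline 60 and ULN 110, a value of 90 would be Grade 0 and 91 would be Grade 2. That is a debatable trade-off, so creatinine remains a note on presentation.

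A reader might infer that both parameters' shift tables will show artefact in place of drug effect. The documents do not support this. Creatinine noise is equal in expectation in the two arms, and in the simulation a true rise still separates them, clearly on the final-value table and with less room on the worst-value table. The GGT problem is confined to one narrow band.

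**Conclusion.** The GGT row is wrong as written: values above 2.0 and up to 2.5 × ULN have no grade, although SAP 9.3.2.2 requires one. This follows from the text and needs no assumption. How many subjects it touches is unknown, and the apparent improvement arises only if ungraded values default to Grade 0.

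For creatinine, the supportable statement is that many Grade 0-to-1 shifts in both arms will reflect within-subject variation. The 83% figure assumes continuous, exchangeable values and all five draws. Over the CVs and two reporting steps tabulated, the worst-value figure runs from 32% to 82%, so no single count per arm should be quoted as expected.

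The point is minor. It affects descriptive Period 1 safety tables only, and has no bearing on efficacy, power, multiplicity, mean-change, Grade 3+ or PCS outputs.

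**What to change.** In the GGT row of Appendix G, end Grade 1 where Grade 2 begins. The ALP row, identical from Grade 2 upward, points to 2.5 × ULN; the sponsor should confirm the value against the cited scale. Use the same bands in the worst-value and final-value tables. The cost is one cell and the matching line of code.

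Optionally, split creatinine Grade 1 shifts into those resting only on the baseline criterion and those above ULN, with a footnote. This leaves the cited scale unchanged and costs one extra table row and minor programming.

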Appendix H. Geographic Region

The following table lists the countries considered for each geographic region.

Geographic Region	Countries
Asia	Israel
Eastern Europe	Estonia, Hungary, Poland
South/Central America	Argentina, Brazil
North America	Canada, United States, Puerto Rico
Other	South Africa, Australia, New Zealand
Western Europe	Belgium, France, Germany, Greece, Italy, Portugal, Spain, United Kingdom, Denmark, Sweden
